If we are able to develop a new triage method that appears to have superior discriminant value to existing methods then we would want to validate this method in a new cohort. A sample including 421 cases with adverse outcome would provide 80% power to compare an area under the ROC curve of 0.85 versus 0.90 at 5% significance, assuming a correlation of 0.6 between scores. We have not included validation of a new triage method in our objectives because this would require (a) successful development of a new method and (b) a much larger sample size, with associated costs and assumptions about pandemic severity. However, if the pandemic is severe (i.e. the prevalence of adverse outcome exceeds 3%, so the number with adverse outcome exceeds 450) we will split the cohort into two equal cohorts to allow testing of existing rules and derivation of new rules on one half and validation of new rules, with comparison to existing rules, on the other.

We plan to collect data across 40 hospitals and have based our sample size calculation on the assumption of receiving 500 completed forms, including an average of 5 adverse outcomes, per hospital over the course of the pandemic.

3 Outcome measures

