5.2 Analysis populations

Name	Participants included
Primary analysis	The adult primary analysis set includes all adults (defined as age 16 or older on the
set (adults)	date of first attendance) for which presence or absence of adverse outcome could be
	ascertained (details of the ascertainment of adverse outcome given in section 8.1.1).
Primary analysis	The child primary analysis set includes all children (defined as age 15 or younger on
set (children)	the date of first attendance) for which presence or absence of adverse outcome could

The following analysis populations will be studied in the analyses:

	be ascerta	be ascertained (details of the ascertainment of adverse outcome given in section		
	8.1.1).			
Secondary	The follow	ing analysis sets will be used in the subgroup analysis detailed in section		
analyses sets	6.7, both will be on adults only due to insufficient numbers in the child cohort:			
	1.	Cases admitted and confirmed as COVID-19 (based on follow up form)		
	2.	Cases admitted and not confirmed as COVID-19 (based on follow up		
		form)		
	3.	Do Not Resuscitate (DNR) decision made on or before day of admission		
	4.	No DNR decision made, or DNR decision made later than day of		
		admission		

6 Outline of analyses

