6.2 Existing triage tools

We will evaluate the following existing triage methods:

- CURB-65 [7]
- PMEWS [8]
- The Swine Flu Hospital Pathway [9]
- NEWS2 [10]

- The WHO decision-making algorithm for hospitalisation with pneumonia [11]
- POPS [12]
- COAST [13]

The triage tools will be retrospectively applied to the data by the study statisticians. CURB-65 and PMEWS will be evaluated in adults only, NEWS2 will be evaluated in adults excluding pregnant women, POPS will be evaluated in children only. Details of scoring and handling missing data for the triage tools are given in sections 8.2 to 8.5. Existing triage tools will be assessed by plotting the ROC curve and calculating the area under the ROC curve (c-statistic) for discriminating between cases with and without adverse outcome. Sensitivity, specificity, positive predictive value and negative predictive value at key decision making thresholds will be calculated and presented:

Tool	Threshold
CURB-65	0-1 versus 2-5
PMEWS	0-2 versus 3+
The Swine Flu Hospital Pathway	0 versus 1+
NEWS2	0-4 versus 5-20, 0-4 versus 50-20 or scoring at least
	3 in one category
WHO	0 versus 1
POPS	0-4 versus 5+
COAST	0-2 versus 3+

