6.5 External validation of prediction models and new triage tools

The population will be split into a development and validation cohort if at least 400 adverse outcomes are recorded (resulting in at least 200 events in each cohort). This will provide sufficient power for the triage tools to be validated [18]. We anticipate there will be insufficient events to split the child cohort and hence this population will not be split. The cohort will be split by date across certain sites. A table of characteristics for the development and validation cohort will be presented to show how the cohorts differ.

The final logistic regression models (both the initial assessment model and full model) will be externally validated by applying the predictive model and triage tools and assessing calibration, discrimination and net benefit in order to assess reproducibility. The validation cohort will also be used to compare the newly developed triage tools against the existing triage tool that performed the best in the development cohort (based on AUROC) by comparing AUROC for these tools.

In order to assess transportability of the new triage tools into different populations or settings, future cohorts must be used to examine heterogeneity in performance across different populations and settings.

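### If the cohort is split, section 2 tests the existing triage tools on one half, although their scores are fixed and the full analysis set would give tighter objective 1 estimates

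*SAP*

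**What the plan says.** Section 2 sets out what happens in a severe pandemic: "so the number with adverse outcome exceeds 450) we will split the cohort into two equal cohorts". The purpose given is "testing of existing rules and derivation of new rules on one half and validation of new rules, with comparison to existing rules, on the other".

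Four other places bear on the population for objective 1, the discriminant value of existing triage methods:

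- Section 5.2: "The adult primary analysis set includes all adults" whose outcome could be ascertained. No half is mentioned.
- Section 2, before the split is introduced: the precision estimates rest on each tool and predictor being tested in the whole cohort. The same section says a more severe pandemic would give more precise estimates at no extra cost.
- Section 6.2: "Existing triage tools will be assessed by plotting the ROC curve" and calculating the c-statistic, with sensitivity, specificity and predictive values at set thresholds. The only restrictions are by age and pregnancy, for example "CURB-65 and PMEWS will be evaluated in adults only, NEWS2 will be evaluated in adults excluding pregnant women". No analysis set and no half is named.
- Section 6.5: the split applies "if at least 400 adverse outcomes are recorded (resulting in at least 200 events in each cohort"), the child cohort is not split, and "The cohort will be split by date across certain sites". In the validation cohort the new tools are compared with the "existing triage tool that performed the best in the development cohort", judged by AUROC.

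**The concern.** A development and validation split guards against optimism, which arises when a model is fitted and judged on the same patients. CURB-65, PMEWS, the Swine Flu Hospital Pathway, NEWS2 and the WHO algorithm come with fixed scoring (sections 8.2 to 8.6) and thresholds set in section 6.2. Nothing about them is estimated from these data, so splitting the cohort gives their accuracy estimates no protection.

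If section 2 is followed literally, objective 1 is answered from half the adults. Validation of a new method, for which the split is made, is something section 2 says is not among the objectives. If sections 5.2 and 6.2 are followed, objective 1 uses everyone. Two statisticians working from this SAP could report different headline c-statistics and sensitivities, and the choice should be fixed before results are seen.

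There is also a smaller mismatch. Section 2 speaks of comparing new rules with existing rules, in the plural, in the second half; section 6.5 compares them with one tool only.

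**Working it through.** **Inputs.** True c-statistic 0.8 and the standard error table (section 2). Split triggers of more than 450 events (section 2) or at least 400 (section 6.5). Two equal cohorts (section 2). A quarter to a third of adverse outcomes in children (section 2, from 2009 data).

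**Reproducing the SAP's table.** The formula SE = √(c(1−c)/events) with c = 0.8, that is √(0.16/events), gives:

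| Events | Computed | SAP |
|---|---|---|
| 150 | 0.0327 | 0.033 |
| 125 | 0.0358 | 0.036 |
| 100 | 0.0400 | 0.040 |
| 75 | 0.0462 | 0.046 |
| 50 | 0.0566 | 0.056 |

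The match is complete apart from truncation in the last row. The Hanley-McNeil formula at 1% prevalence gives 0.0218 for 150 events, so it is not what the SAP used.

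**Full set against one half, same formula, equal halves.**

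| Trigger | Events, all / half | SE, all / half | 95% half-width (1.96 × SE), all / half |
|---|---|---|---|
| Section 2 | 450 / 225 | 0.0189 / 0.0267 | 0.037 / 0.052 |
| Section 6.5 | 400 / 200 | 0.0200 / 0.0283 | 0.039 / 0.055 |

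The ratio is √2 = 1.41 in both rows. It does not depend on the variance formula: Hanley-McNeil at 3% prevalence gives 0.0126 and 0.0179 for 450 and 225 events, again a ratio of about 1.4. If a split by date gives unequal cohorts, with a fraction f of the events in the development cohort, the ratio becomes 1/√f.

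**Sensitivity.** The half-width is 1.96 × √(s(1−s)/events):

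- s = 0.95: 0.020 on 450 events, 0.028 on 225. Exact lower 95% limits are 0.927 and 0.914.
- s = 0.80: 0.037 on 450 events, 0.052 on 225.

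**Adult-only tools.** Section 2's 450 counts all ages. If a quarter to a third of events are in children, adult events number 450 × 2/3 = 300 to 450 × 3/4 ≈ 338, or 150 to 169 per half. The standard error is then √(0.16/300) = 0.0231 to √(0.16/338) = 0.0218 on all adults, against √(0.16/150) = 0.0327 to √(0.16/169) = 0.0308 on a half. The ratio is unchanged.

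**Against the planning target.** Section 2 plans on 150 events (SE 0.033). A half with 225 or 200 events exceeds this, and an adult half with 150 to 169 just meets it. If section 6.5's 400 were counted over all ages, an adult half would hold 400 × 2/3 ÷ 2 ≈ 133 to 400 × 3/4 ÷ 2 = 150. However, section 6.5 expects at least 200 events per cohort and does not split children, which points to 400 adult events.

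**The case against.** The strongest reply is that the passages can be read together. Section 5.2 says who is eligible, and section 6.5 later divides those people; an eligibility definition does not forbid a partition. Section 6.2 is silent on the split, so it does not contradict section 2 outright. The whole-cohort sentence in section 2 leads into separate tools for adults and children, not into the split. All of this is fair. What remains is that no sentence says which population gives the headline objective 1 results after a split, and the only sentence that speaks to it points to one half.

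A reader might infer that the halving serves no purpose. The SAP does not support that. Section 6.5 uses the development-cohort AUROC to pick the comparator, so that it is not chosen and tested on the same patients. That justifies computing a development-half AUROC for selection; it does not justify confining the headline accuracy estimates to that half.

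A reader might also infer that the other half is lost to the existing tools. It is not: section 2 compares existing rules with new ones there, although section 6.5 narrows this to one tool. Nor is objective 1 left short of its planned precision on the event counts that sections 2 and 6.5 give for each half.

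On the plural against the single comparator, section 6.5 can fairly be read as the operational detail behind a one-sentence outline. The two should agree, but reporting every paired AUROC difference would be a matter of preference.

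**Conclusion.** The point holds as an unresolved population for objective 1 after a split, with an avoidable loss of precision if section 2 is taken at its word. With equal halves, standard errors and interval widths are about 1.41 times larger than the collected data allow: 0.0267 against 0.0189 for a c-statistic of 0.8 at 450 events, with correspondingly fewer events for adult-only tools. No bias is involved, the loss arises only if the split is triggered, and a half of the 450-event cohort still meets the 150-event planning target.

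The figures rest on the variance formula that reproduces the SAP's table, on equal halves, and, for the adult-only range, on the 2009 share of events in children. The conclusion that no split is needed rests on the tools' scores and thresholds being fixed in advance, as sections 6.2 and 8 set out.

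**What to change.** - In sections 2 and 6.2, state that the headline existing-tool estimates (AUROC, sensitivity, specificity, predictive values) use the full adult and child primary analysis sets, subject to each tool's own age and pregnancy restrictions, whether or not the cohort is split.
- State that AUROCs of existing tools in the development cohort serve only to choose the comparator for section 6.5.
- Keep the univariable and functional-form work that informs model building within the development cohort. Section 7.2 uses univariate results to decide which non-linear terms are considered for the LASSO model, so running that work on the full set would let validation data into model building.
- Make section 2 and section 6.5 agree on whether the validation comparison is with one existing tool or several. The two split triggers (more than 450 events, at least 400) can be aligned in the same edit.

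The cost is a few sentences in the SAP and a few more lines of output. No extra data are needed.

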3.1 Primary outcome

Patients who die or require respiratory, cardiovascular or renal support within 30 days of first attendance will be defined as having an adverse outcome. If patients survive to 30 days without requiring respiratory, cardiovascular or renal support they will be defined as having no adverse outcome. A detailed description of how adverse outcome is determined using study data, including the handling of missing data is given in section 8.1.1.

3.2 Secondary outcomes

The following secondary outcomes will be investigated

- Death without respiratory, cardiovascular or renal support: This outcome is less likely to have been preventable, since it either occurred before intervention was possible or intervention was not expected to be beneficial.
- Respiratory, cardiovascular or renal support as a composite outcome (i.e. excluding group 1 above): This outcome is more likely to represent a preventable or prevented death, since life-saving intervention was attempted.
- Subsequent admission, or adverse outcome, in the cohort of adult patients discharged at initial attendance (excluding discharged with DNR decision). This outcome would enable investigation into whether we can predict risky discharge decisions.

The analysis to be performed on these secondary outcomes is given in section 6.8.

4 Weekly descriptive analysis

Whilst study data is being collected, weekly descriptive reports, created by the study statisticians will be produced.

The following will be included in the weekly reports

- 1. The number and geographical distribution of new cases
- 2. The proportion with an adverse outcome and details of adverse outcomes
- 3. Summaries of characteristics and potential prediction factors presented for
 - a. The whole cohort
 - b. Patients with adverse outcome
 - c. Patients who were not admitted but had adverse outcome
 - d. Patients who were admitted but did not have adverse outcome
- 4. Detailed line listings of patients who were not admitted but did have adverse outcome

The report will be made available to the study team, the Project Management Group (PMG) and the Study Steering Committee (SSC). However, the PMG and SSC may only see the report for the week they are meeting.

5 Data Sources and analysis populations

5.1 Data sources

Study data will be extracted from source documents and entered onto the CTRUs in house data management system (PROSPECT). The data management team in the Sheffield CTRU will provide limited post-entry validation (as stipulated in SOP DM005). The trial statistician will conduct any additional validation checks where appropriate before the data lock and sign off (as guided by DM005 and DM012).

Table 1: Details of data collected at each timepoint

Baseline	Pandemic Respiratory Infection Form
Baseline 2	Pandemic Respiratory Infection Form
Baseline 3	Pandemic Respiratory Infection Form
Follow up (30 days after Baseline)	Follow up

5.1.1 Study population and Inclusion/exclusion criteria

Planned inclusion/exclusion criteria are detailed in the protocol. For the adults and children presenting at recruiting hospital emergency departments, inclusion will be determined on the basis of the assessing clinician recording on the patient record that the patient has suspected pandemic infection, which will result in standardised data being collected.

5.2 Analysis populations

Name	Participants included
Primary analysis	The adult primary analysis set includes all adults (defined as age 16 or older on the
set (adults)	date of first attendance) for which presence or absence of adverse outcome could be
	ascertained (details of the ascertainment of adverse outcome given in section 8.1.1).
Primary analysis	The child primary analysis set includes all children (defined as age 15 or younger on
set (children)	the date of first attendance) for which presence or absence of adverse outcome could

The following analysis populations will be studied in the analyses:

	be ascerta	be ascertained (details of the ascertainment of adverse outcome given in section		
	8.1.1).			
Secondary	The follow	ing analysis sets will be used in the subgroup analysis detailed in section		
analyses sets	6.7, both will be on adults only due to insufficient numbers in the child cohort:			
	1.	Cases admitted and confirmed as COVID-19 (based on follow up form)		
	2.	Cases admitted and not confirmed as COVID-19 (based on follow up		
		form)		
	3.	Do Not Resuscitate (DNR) decision made on or before day of admission		
	4.	No DNR decision made, or DNR decision made later than day of		
		admission		

6 Outline of analyses

6.1 General considerations

Summaries of continuous variables will comprise the number of observations used, mean, median, standard deviation, inter-quartile range, minimum and maximum as appropriate for the distributional form of the data.

Summaries of categorical variables will comprise the number of observations used, and the number and percentage of observations in each category.

For all analyses the patient, rather than the attendance, will be the unit of analysis. If patients attend more than once (the database can collect up to three 'baseline' attendances) and have predictor variable data recorded on more than one occasion, we will only use the predictor variable data from the first attendance in all analyses.

Complete details of data derivations and methods of handling missing data are covered in section8.

6.2 Existing triage tools

We will evaluate the following existing triage methods:

- CURB-65 [7]
- PMEWS [8]
- The Swine Flu Hospital Pathway [9]
- NEWS2 [10]

- The WHO decision-making algorithm for hospitalisation with pneumonia [11]
- POPS [12]
- COAST [13]

The triage tools will be retrospectively applied to the data by the study statisticians. CURB-65 and PMEWS will be evaluated in adults only, NEWS2 will be evaluated in adults excluding pregnant women, POPS will be evaluated in children only. Details of scoring and handling missing data for the triage tools are given in sections 8.2 to 8.5. Existing triage tools will be assessed by plotting the ROC curve and calculating the area under the ROC curve (c-statistic) for discriminating between cases with and without adverse outcome. Sensitivity, specificity, positive predictive value and negative predictive value at key decision making thresholds will be calculated and presented:

Tool	Threshold
CURB-65	0-1 versus 2-5
PMEWS	0-2 versus 3+
The Swine Flu Hospital Pathway	0 versus 1+
NEWS2	0-4 versus 5-20, 0-4 versus 50-20 or scoring at least
	3 in one category
WHO	0 versus 1
POPS	0-4 versus 5+
COAST	0-2 versus 3+

6.3 Presenting clinical characteristics and routine tests

For all characteristics (candidate predictors) we will present the odds ratio, p-value and 95% confidence interval (CI) from a univariable analysis. For binary characteristics we will also present the distribution of adverse outcomes in each category. If a continuous characteristic has pre-specified cut-off points the distribution of adverse outcomes will be presented for each category.

The following clinical characteristics and routine tests will be evaluated.

Continuous Characteristic	Cut offs	Adults	Children	Initial assessment model	Full model
Age	None	\checkmark	\checkmark	\checkmark	\checkmark

Symptom duration		✓	~	✓	✓
Number of current		1	1	√	√
medications		·		·	·
Urea		√	✓		✓
Creatinine		√	~		✓
Respiratory rate	0= 12-20 or missing 1= 9-11	1			
	2= 21-24 3= <9 or >24	·	v	· ·	· ·
Pulse rate	0= 51-90 or missing 1= 41-50 or				
	91-100 2= 111-130 3= <41 or	\checkmark	~	~	\checkmark
	>130				
Temperature	0= 36.1-38.0 or missing 1= 35.1-				
	36.0 or 38.1-39.0 2= >39.0 3=	✓	✓	~	✓
	<35.1				
Systolic Blood	0= 111-219 or missing 1=101-				/
Pressure	110 2= 91-100 3= <91 or >219	v	v	v	v
SaO ₂	0= >95 or missing 1= 94-95 2=				
	92-93 3= <93 (add two points	✓	✓	✓	\checkmark
	for FiO ₂ >21%)				
SaO ₂ /FiO ₂ ratio		✓	✓	√	✓
GCS Total ^a	1= Severe (<8) 2= Moderate (9-				/
	12) 3= Mild (13-15)	v	v	v	v
Na	1= Low (<136) 2=Normal (136-				
	142) 3 = High (>142)	v	v		v
К	1= Low (<3.5) 2=Normal (3.5-				
	5.0) 3 = High (>5.0)	v	v		v
Hb	1= Low (<130 males, <115				
	females) 2=Normal (130-180				/
	males, 115-165 females) 3 =	v	v		v
	High (>180 males, 165 females)				
Platelets	1= Low (<150) 2=Normal (150-				/
	400) 3 = High (>400)	v	v		v
WCC	1= Low (<4) 2=Normal (4-11) 3	1	1		
	= High (>11)	V	V		V
Neutrophils	1= Low (<2.0) 2=Normal (2.0-				
	7.5) 3 = High (>7.5)	V	V		V
Lymphocytes	1= Low (<1.5) 2=Normal (1.5-				
	4.5) 3 = High (>4.5)	~	×		√
Lactate		✓	✓		~

C-Reactive	~	~	~
D-dimer	~	~	~
Troponin	~	~	~

a) Both GCE and AVPU will be analysed in univariable analysis, however in multivariable analysis AVPU will be used and missing AVPU data will be imputed using GCE scores (see section 7.1.2 for the imputation rules).

Binary				Initial	
Characteristic	Levels	Adults	Children	assessment	Full model
enaracteristic				model	
Sex	Male/Female	~	~	~	\checkmark
Presenting features	Presence/Absence per feature				
(Shortness of breath,					
cough, fever, sore					
throat, headache,		1	1	 	1
confusion, rash,		·	•		•
anosmia, abdominal					
pain, diarrhoea,					
vomiting)					
Previous attendance	Yes/No	✓	~	~	✓
Current use of	Presence/Absence				.(
anticoagulants		v	v	· ·	v
Medical History	Yes/No per disease				
(Heart disease, renal					
impairment, steroid					
therapy, asthma,					
diabetes, active		1		1	
malignancy,		·	·	•	•
immunosuppression,					
other chronic lung					
disease,					
hypertension)					
Paediatric questions	Yes/No per question		~	~	\checkmark
(routine vaccination,					
taking feeds,					
parental anxiety,					
premature)					
known contact with	Yes/No per lifestyle option	~	~	 	 
Covid-19 case					÷

Lifestyle (Pregnant,	Yes/No per lifestyle option				
clinically obese,		~		\checkmark	\checkmark
tobacco/vape user)					
Central capillary	Normal/Abnormal	1	✓	✓	✓
refill					
Severe respiratory	Yes/No	~	✓	✓	✓
distress					
Respiratory	Yes/No	✓	\checkmark	\checkmark	\checkmark
exhaustion					
Severe dehydration	Yes/No	✓	\checkmark	\checkmark	\checkmark
CXR	Normal/Abnormal*	~	~		~
ECG	Normal/Abnormal*	~	~		✓

* May also be treated as categorical with normal/abnormal/not done depending on frequencies

Categorical Characteristic	Levels	Adults	Children	Initial assessment model	Full model
Ethnicity*	UK/Irish/other white				
	-South Asian				
	-East Asian				
	-Other Asian				
	-Arab	\checkmark	\checkmark	\checkmark	✓
	-African				
	-Caribbean				
	-Other black				
	-Other/Mixed				
Performance	1=Unrestricted normal activity				
status*	2=Limited strenuous activity, can do				
	light 3=Limited activity, can self	~	✓	~	~
	care 4=Limited self care				
	5=Bed/chair bound, no self care				

*We will consider combining similar categories to reduce the number of predictor variables in the model (each category counts as one predictor), particularly ethnicity where some categories may have low frequencies.

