1.1 Study objectives

The specific objectives outlined in the protocol after each wave of the pandemic, for the hospital (emergency department) are:

- 1. To determine the discriminant value of emergency department triage methods for predicting severe illness in patients presenting with suspected pandemic respiratory infection
- 2. To determine the discriminant value of presenting clinical characteristics and routine tests for identifying severe illness
- 3. To determine the independent predictive value of presenting clinical characteristics and routine tests for severe illness
- 4. To develop new triage methods based upon presenting clinical characteristics alone or presenting clinical characteristics, electrocardiogram (ECG), chest X-ray and routine blood test results, depending upon the data available and the predictive value of variables evaluated in objective 3

2 Sample Size

The sample size will ultimately depend upon the size and severity of the pandemic. Our pragmatic data collection methods will ensure that we maximise any opportunity to evaluate emergency department triage methods in a pandemic.

Our experience in the 2009 pandemic has shown us that pre-pandemic estimates of case hospitalisation and case fatality rates can be very misleading and that sample size estimates must take into account considerable uncertainty in these estimates. Nevertheless, we have also shown that informative findings can be generated even in a pandemic with a very low rate of adverse outcome.

Given that most cases of suspected pandemic respiratory infection (even in a severe pandemic) do not result in an adverse outcome, the key variable in determining study power is the number of cases with an adverse outcome. A single cohort including at least 150 cases with adverse outcome would allow us to estimate the c-statistic of a triage method, clinical variable or test with a standard error of 0.03 (assuming the true c-statistic was 0.8). The table below shows the standard error resulting from samples with smaller numbers of adverse outcomes.

N with adverse outcome	Standard error (assuming c-statistic was 0.8)
150	0.033
125	0.036
100	0.040
75	0.046
50	0.056

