A sample with N=150 adverse outcome would estimate the sensitivity of a dichotomised rule, variable or test with a standard error as outlined in the table below, depending on the sensitivity at the threshold used. Estimates of specificity would obviously be very precise given the anticipated low prevalence of adverse outcome.

Sensitivity	Lower limit of 95% Cl
1.00	0.98
0.95	0.90
0.90	0.84
0.85	0.78
0.80	0.73

The same cohort could be used to identify independent predictors of outcome and develop new triage methods (objectives 3 and 4). The number of variables that could be tested as independent predictors of outcome in a multivariable model and for inclusion in a triage method would depend upon the sample size. Based on the rule of thumb of needing at least 10 events for each independent regression variable in a

logistic regression, a cohort with 150 cases with adverse outcome would allow us to test up to 15 parameters [4].

These estimates assume that each triage method and predictor variable will be used and tested on the whole cohort. However, we plan to explore whether different patients require different triage methods, particularly whether a different triage method is required for children and adults. Data from the 2009 H1N1 pandemic suggest that around a quarter to a third of adverse outcomes may occur in children [5] [6]. To increase the probability that we will have at least 50 cases with adverse outcome among children we will aim to recruit a total of 200 cases with adverse outcome rather than 150.

If we assume that the prevalence of adverse outcome is the same as our 2009 cohort (1%) then we would need to collect data from 20,000 cases to identify 200 with an adverse outcome. We have therefore used this estimate in planning, although it is likely to be an overestimate of the total numbers required given the mild nature of the 2009 pandemic. A more severe pandemic would allow more precise estimates to be made with no additional costs or would allow us to reduce the total number of cases required to identify 200 with an adverse outcome.

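### Section 6.3 specifies no discrimination measure for single characteristics and tests, although objective 2 asks for one and section 2 plans precision on one

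*SAP*

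**What the plan says.** Section 1.1 lists as objective 2 "To determine the discriminant value of presenting clinical characteristics and routine tests for identifying severe illness". Objective 3 is separate: "To determine the independent predictive value of presenting clinical characteristics and routine tests for severe illness". Objective 1 uses the same term as objective 2, discriminant value, for the existing triage methods.

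Section 2 carries that term into the sample size. A cohort with 150 adverse outcomes is said to "estimate the c-statistic of a triage method, clinical variable or test with a standard error of 0.03" at a true value of 0.8, and it "would estimate the sensitivity of a dichotomised rule, variable or test with a standard error as outlined in the table below". Both statements name single variables and tests, not only triage tools.

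Section 6.2 meets objective 1 with ROC curves, c-statistics, sensitivity, specificity and predictive values. Section 6.3 covers the single characteristics. There the SAP says "we will present the odds ratio, p-value and 95% confidence interval (CI) from a univariable analysis". Two additions follow: "For binary characteristics we will also present the distribution of adverse outcomes in each category", and "If a continuous characteristic has pre-specified cut-off points the distribution of adverse outcomes will be presented for each category". The only other c-statistic for a fitted model is in section 7.3.3, under prognostic model checking. Section 6.4 states that univariable screening will not decide which predictors enter the model.

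**The concern.** The measure that the objective names, and on which the cohort was sized, is missing from the section that should deliver it. An odds ratio describes association. For a continuous variable it depends on the unit, and for a binary one it does not fix discrimination unless the prevalence of the sign is also known. A p-value depends on the number of events as well as on the strength of the relationship.

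If the SAP is followed as written, several obvious triage candidates (age, the SaO2/FiO2 ratio, urea, lactate, C-reactive protein) would be reported on a scale that cannot be set beside the c-statistics of the tools in section 6.2. A reader could not tell from the planned output whether one measurement discriminates nearly as well as a whole score.

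**Working it through.** **1. The plan's own precision figures.** Inputs from section 2: c-statistic A = 0.8 and 150, 125, 100, 75 or 50 adverse outcomes. With SE = sqrt(A(1 − A)/n):

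| n events | Computed SE | SAP |
|---|---|---|
| 150 | sqrt(0.16/150) = 0.0327 | 0.033 |
| 125 | 0.0358 | 0.036 |
| 100 | 0.0400 | 0.040 |
| 75 | 0.0462 | 0.046 |
| 50 | 0.0566 | 0.056 |

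The table reproduces, apart from truncation in the last row. The formula is an upper bound when events are the smaller group; the Hanley–McNeil formula at 1% prevalence gives 0.0218 at 150 events and 0.0378 at 50. The sensitivity table also reproduces to about 0.01: Clopper–Pearson lower limits at n = 150 are 0.976, 0.898, 0.840, 0.786 and 0.727, against 0.98, 0.90, 0.84, 0.78 and 0.73. So the precision statements are sound, and they concern discrimination.

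**2. What section 6.3 delivers, adult list.**

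- Continuous with listed cut-offs, 13: respiratory rate, pulse, temperature, systolic pressure, SaO2, GCS, Na, K, Hb, platelets, WCC, neutrophils, lymphocytes. Outcome distribution planned.
- Binary, 33: sex 1, presenting features 11, previous attendance 1, anticoagulants 1, medical history 9, contact with a case 1, lifestyle 3, clinical signs 4, CXR and ECG 2. Outcome distribution planned.
- Continuous without cut-offs, 10: age, symptom duration, number of medications, urea, creatinine, SaO2/FiO2 ratio, lactate, C-reactive protein, D-dimer, troponin. Neither a distribution nor a discrimination measure.
- AVPU (added by the table footnote), ethnicity and performance status, 3: neither stated.

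Total 13 + 33 + 10 + 3 = 59. A distribution is planned for 13 + 33 = 46 and not for 10 + 3 = 13. A c-statistic, sensitivity or specificity is specified for none. The child list differs only in dropping the three lifestyle items and adding four paediatric ones, with one tick (lymphocytes) unclear in the text available.

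**3. Why the odds ratio cannot stand in.** For a binary sign present in a proportion p0 of non-events and p1 of events, odds(p1) = OR × p0/(1 − p0) and c = 0.5 + (p1 − p0)/2. With OR = 5:

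- p0 = 0.02: odds = 5 × 0.02/0.98 = 0.102, p1 = 0.093, c = 0.536.
- p0 = 0.30: odds = 5 × 0.30/0.70 = 2.143, p1 = 0.682, c = 0.691.

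For a continuous variable, rescaling the unit by a factor k turns OR into OR^k but leaves the ranking of patients, and so the c-statistic, unchanged.

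**4. Can the planned events support the missing measure?** By the SAP's own method at c = 0.8, the 95% half-width is 1.96 × 0.0327 = 0.064 with 150 events and 1.96 × 0.0283 = 0.055 with 200. If 50 of the 200 planned events fall in children, as section 2 hopes, the half-width there is 1.96 × 0.0566 = 0.111. Missing blood results would widen these intervals.

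**The case against.** The best defence is that little depends on section 6.3. The models are built by LASSO from all candidate predictors, so a missing univariable c-statistic alters no model, tool or primary conclusion. That stands, and it limits the point to the reporting of objective 2.

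Second, section 6.3 is not silent. Outcome distributions, with the numbers and percentages that section 6.1 requires, let a reader derive sensitivity and specificity for 46 of the 59 adult characteristics. This also stands, though the intervals are left unspecified and the other 13 are not helped. The weekly reports in section 4 summarise characteristics for the whole cohort and for patients with an adverse outcome, but these are running descriptive reports, and means or medians do not yield a c-statistic.

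Third, section 7.3.3 promises a c-statistic for each logistic model, and a univariable logistic regression is one. Its place under prognostic model checking makes that reading strained.

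Fourth, a raw c-statistic is undefined for nominal ethnicity and can understate discrimination where risk may rise at both ends of the scale. This is right, and the fix allows for it.

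Two stronger readings are tempting. A reader might infer that 59 adult p-values, and about as many in children, form an uncontrolled family of tests. The SAP does not support this: section 6.3 sets no significance level and attaches no claim to the p-values, section 6.4 bars univariable screening, and 5% significance appears only for comparing ROC areas in a validation cohort. A reader might also infer that objective 2 goes unanswered. That is too broad, given the planned distributions.

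**Conclusion.** The mismatch is real and can be read from the SAP alone. Objective 2 and section 2 speak of discrimination by single variables and tests; section 6.3 specifies only measures of association, with distributions for some variables.

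The gap is complete for the ten continuous variables without cut-offs. It applies equally to AVPU, ethnicity and performance status, for which no outcome distribution is stated in section 6.3. It is partial for the 46 binary and cut-off variables in adults, where sensitivity and specificity are derivable but not specified with intervals. This rests on reading section 7.3.3 as covering the prediction models only, and on the planned distributions showing counts.

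The consequence is an objective reported partly on the wrong scale, not a biased or invalid analysis. There is no error-rate problem in section 6.3 to correct.

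**What to change.** In section 6.3:

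- Add the c-statistic with 95% CI for each continuous, ordinal and binary characteristic.
- For ethnicity, and for variables whose risk may rise at both ends (for example temperature, pulse and systolic pressure), take the c-statistic from the fitted univariable model, using the categories or the non-linear form of section 7.2. Say that this has been done, since the ordering then comes from the same data.
- Add sensitivity and specificity with 95% CI for binary and pre-categorised variables, naming the split used where there are more than two categories.
- Keep the odds ratio with its CI. State that the univariable results are descriptive; the p-values may stay or go.

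The cost is a few sentences in the SAP and a few output columns from data already being analysed. No extra patients or data items are needed, and no multiplicity adjustment. Intervals in children will be wide, and the report should show them as such.
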